15.7. Independent Clinical Events Committee

The members of the ICEC will be experienced clinicians in the care of PAH subjects and experienced in adjudication for clinical trials in PAH. The ICEC will review and adjudicate the following:

- All SAEs
- Rebound PH
- Subject eligibility when eligibility may be unclear

An independent research organization experienced in the adjudication of cardiovascular events will supervise the collection of data on all events. They will maintain a website where the committee members can access the data, determine the need for more data, and record their findings. The research organization will coordinate all ICEC meetings and be responsible for transferring the adjudication data to the Sponsor.

The data presented to the ICEC members will be reviewed and any information that may lead to un-blinding of the reviewer will be removed.

The Sponsor, appointed research organization, and ICEC will create a pre-determined SMQ list to capture all potential event terms that may be reported and attributed to PAH. Once all parties come to agreement on the list, the electronic adjudication system (EAS) will be programmed to identify potential events for adjudication based on the SMQ list. All AEs will be imported into the EAS and compared against the SMQ programmatically. Events will be managed on a daily basis by adjudication staff. Adjudication staff will collect essential elements for review by the ICEC.

An ICEC charter will be developed with input from the ICEC members, the steering committee, research organization and the Sponsor.

16. STATISTICAL CONSIDERATIONS

This section provides a general description of the statistical methods to be used in analyzing both safety and efficacy data. The key statistical issues or considerations will be addressed. A more detailed statistical analysis plan will be provided in a separate document that will be finalized before unblinding of treatment assignment.

Unless otherwise specified, all statistical tests will be one-sided with a significance level of 0.025. Summary statistics will be provided for all study variables with descriptive statistics (number of observations, mean, standard deviation, median, minimum, and maximum) for numerical (or continuous) variables and with frequency and percentage for categorical variables.

All statistical analysis will be conducted using SAS version 9.2 or higher (SAS Institute Inc., Cary, NC).

16.1. Population(s) for Analysis

An intent-to-treat (ITT) population that consists of all randomized subjects who remained eligible after the Run-in period will be used for all the efficacy analyses: subjects will be analyzed in the treatment group to which they were randomized

A safety population that includes all randomized subjects who receive the study treatment and who remained eligible after the Run-in period will be used for all the safety analyses. In addition, an analysis of safety for all randomized subjects who receive the study treatment and who became ineligible after the Run-in period will be conducted. For the safety population, subjects will be summarized according to the treatment they received during the study.

16.2. Sample Size Determination

Interim Analysis will be conducted by an independent DMC after 18-week 6MWD data are available from 75 patients. The purpose of the interim analysis is to stop the trial for an early efficacy or futility conclusion or to continue the trial to 150 or 188 - patients (total randomized is higher to account for an anticipated 20% dropout rate). Group sequential early stopping criteria and sample size re-estimation methodology are further described in the statistics section of this protocol. They are constructed to control overall type 1 error at 0.025, 1-sided. Simulations assuming true underlying mean treatment difference in 6MWD ranging from 30-70 meters and standard deviations from 50 to 75 meters yielded >87% power for all cases except the most extreme case (mean difference 30 meters and SD 75), for which power was ~71%.

Subjects who do not comply with the required device adherence, as well as who do not meet the study entry criteria at Week 2, will be withdrawn from the study.

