The primary statistical test for the primary endpoint will be performed using a repeated measures mixed model with the baseline stratification factor (i.e., the prostanoid usage status) treatment arm, week and treatment-by-week as the fixed effects. As a covariate, baseline 6MWD assessment (defined by the average of two 6MWTs at Week 2 after the completion of the run-in phase) will be included in the model. In case the normality assumption is invalid, the primary efficacy endpoint will be analyzed using the van Elteren test stratified by the prostanoid usage status. Summary statistics will be provided for all study variables with descriptive statistics (number of observations, mean, standard deviation, median, minimum, maximum and from the analysis model the least squares means, SAE's and confidence limits) for numerical (or continuous) variables and with frequency and percentage for categorical variables.

Exploratory analyses will be performed to evaluate the effects of demographics and baseline characteristics on the efficacy response with appropriate statistical methods. Subgroup analyses based on study drug usage, background therapies, demographics and baseline characteristics, as well as other study compliance status will be conducted. Additional statistical methods such as mixed effects model and Cochran-Mantel-Haenszel (CMH) test (for dichotomized response analysis) may be utilized in the exploratory analyses.

Interim analyses will be conducted when data is available from 75 patients. The purpose of the interim analysis is to stop the trial early for efficacy or futility or to continue the trial to 150 or 188 patients (total randomized is higher to account for an anticipated 20% drop out rate). Group sequential early stopping criteria and sample size re-estimation methodology are further described in the statistics section of this protocol. They are constructed to control overall type 1 error at 0.025, 1-sided.

Simulations assuming true underlying mean treatment difference in 6MWD ranging from 30-70 meters and SD's from 50 to 75 meters yielded >87% power for all cases except the most extreme case (mean difference 30 meters and SD 75, for which power was ~71%.

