8.2. Treatment Assignment

Subjects who meet all enrollment criteria during the Screening period will be randomized in a 1:1 ratio into one of two dosing cohorts as presented in [Table 1](#). Ninety-four subjects will be enrolled in each cohort.

[figure not shown]
Table 1: Dosing Assignments for Run-in and Treatment Periods

	Part 1 Blinded Treatment Period		Part 2 Open Label Period
Cohort	Run-in Period Week 0 to Week 2	Treatment Period Week 3 to Week 18	Open Label Treatment
Cohort 1: Placebo	Placebo at a dose setting of 15 mcg/kg IBW/hr	Placebo at a dose setting of 75 mcg/kg IBW/hr	iNO 75 mcg/kg IBW/hr
Cohort 2: iNO 75 mcg/kg IBW/hr	iNO 15 mcg/kg IBW/hr	iNO 75 mcg/kg IBW/hr	iNO 75 mcg/kg IBW/hr

Note: Study drug is dosed according to IBW and not actual body weight. IBW is determined by a subject's gender and height, and therefore will not change during the study period.

A study flow diagram is presented in [Figure 1](#).

Figure 1: Study Design

*All subjects during the Run-in period must be willing to comply with usage of INOpulse device for ≥ 12 hours (rounded to the nearest hour) per day, with no more than 2 days of usage < 8 hours per day. Subjects randomized to iNO will receive 15 mcg/kg IBW/hr for the first 2 weeks (Run-in phase) followed by iNO at 75 mcg/kg IBW/hr dose for the Treatment Period. Subjects randomized to Placebo will receive Placebo product 15 mcg/kg IBW/hr at a delivery setting matching the treatment groups.

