16.5. Interim Analysis

A formal interim analysis is planned in this study as follows:

1. Stop for futility (null hypothesis is accepted; there is no difference between iNO and Placebo).
2. Stop for efficacy (null hypothesis is rejected; there is difference between iNO and Placebo favoring iNO).
3. Sample size determination (decision to use blinded or unblinded data).
4. Stop in case of safety concerns. Safety concerns may be some imbalances in adverse events frequency which is not in favor of iNO. No formal statistical guideline is provided for this purpose, the sponsor relies on the medical expertise of DMC members.
5. Continue the trial with the planned sample size until next stage if point 1, 2 or 4 not apply.

The following two designs will define the interim analysis strategy:

- 1) Design 1: Groups Sequential Design (for efficacy part)
- 2) Design 2: Sample Size Re-estimation (SSR) (for futility and sample size re-estimation)

The interim analysis schedule planned as follows:

Schedule	Requirement
1st	After 75 patients complete 18 Weeks of blinded treatment phase.
Final	After 150/188 (depending on CP and PP) patients complete 18 Weeks of blinded treatment phase.

Traditional group sequential design (GSD) alpha spending function $\Gamma = -3$ (Hwang, Shih, deCani, 1990) is used to control the overall type 1 error at 0.025, 1-sided. The interim analysis rule (Table 7) is as follows.

Table 7: Interim and Final Analysis Rules

Category	Rule
Efficacy	At first interim analysis (after 75 patients), if the one-sided $p < 0.0046$ then the study will stop for efficacy (Wald Statistics)
Efficacy	At final analysis (after 150 patients or 188 patients depending on CP and PP), if the one-sided $p < 0.0229$ then the study will yield an efficacy conclusion. (based on CHW Statistics)
Futility	If conditional power (CP) or predictive power (PP) $\leq 10\%$ then the study stops for futility.
Continue	If $10\% < CP$ and $PP < 30\%$ then trial continues to 150 patients.
SSR	If $30\% \leq CP$ or $PP < 80\%$ then the sample size required to boost the CP or PP to 80% is computed. If this sample size exceeds 188 (upper limit) then the study continues at $N = 150$ else to 188.
Continue	If CP and $PP \geq 80\%$ then the trial continues to $N = 150$ patients

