## 5.4 Sample Size

The sample size calculation for this study was performed assuming one interim analysis. The purpose of the interim analysis is to stop the trial for efficacy or futility conclusion or to continue the trial to 150 or 188 patients.

The sample size calculations were performed using following two designs:

- 1) Design1: Group sequential early stopping criteria and
- 2) Design 2: Sample size re-estimation methodology

Design 1: Traditional group sequential design (GSD) alpha spending function  $\Gamma=3$  ([Hwang, Shih, deCani, 1990](#)) is used to control the overall type 1 error at 0.025, 1-sided.

Design 2: This is the "promising zone" sample size re-estimation (SSR) design of [Mehta & Pocock \(2011\)](#), which uses the [Cui, Hung, Wang \(1999\)](#) method of analysis to combine the test statistics for the separate analyses of the IA and post-IA parts of the trial, if the trial does not stop at IA.

The final analysis is via weighted Z statistic using equal weights for the IA and post IA test statistics. It requires  $p < 0.0229$  1-sided for statistical significance to control the overall type 1 error level at 0.025 1-sided with  $\Gamma=3$  error spending function ([Hwang, Shih, deCani 1990](#)).

A sample size of 150 patients (75 in each group) with simulations assuming true underlying mean treatment difference in 6MWD ranging from 30-70 meters and standard deviation from 50-70 meters yielded  $> 87\%$  power for both designs (for all cases except the most extreme case (mean difference of 30 meters and S.D 75, power for this combination was 71%).

The estimated conditional power (CP) and predictive power (PP) based on interim estimated SD and mean differences observed on 75 subjects with a planned final sample size of 150 is shown in ([Table 22](#)).

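### The interim rules as written give about 83–84% power at 30 m/SD 60 and about 64–66% at 30 m/SD 75, not the stated >87% and ~71%

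*Protocol*

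**What the plan says.** **Power.** Protocol section 16.2 describes "Simulations assuming true underlying mean treatment difference in 6MWD ranging from 30-70 meters and standard deviations from 50 to 75 meters" and says they "yielded >87% power for all cases except the most extreme case (mean difference 30 meters and SD 75), for which power was ~71" per cent. The synopsis repeats that they "yielded >87% power for all cases except the most extreme case". SAP section 5.4 claims the same for both designs (group sequential and re-estimation). It gives the SD range as 50–70 m but names 30 m/SD 75 as the exception: "power for this combination was 71" per cent. None of the three places says whether the futility stop was active in the simulations.

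**Interim look.** "Interim Analysis will be conducted by an independent DMC after 18-week 6MWD data are available from 75 patients". Protocol Table 7 and SAP Table 35 share these rules:
- efficacy stop at one-sided p<0.0046;
- final test at p<0.0229 on an equally weighted Cui-Hung-Wang (CHW) statistic;
- if CP or PP is 10% or less, "then the study stops for futility".

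Neither table calls the futility rule optional or non-binding.

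**Sample size increase.** The tables differ. Protocol Table 7 has a zone from 30% to 80% and goes to 188 only if 188 is enough to reach 80%; otherwise the trial stays at 150. SAP Table 35 has a zone from 57.2% to 80% and always goes to 188 within it.

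**The concern.** A trial stopped for futility cannot succeed, so the power of this design has to include the stop. At the low end of the sponsor's own effect range, the stop removes trials that would otherwise have continued, some of them to success. If the stated figures do not count that loss, the sponsor, the DMC and ethics committees are told that only one assumed scenario falls below 87%, when under the written rules a second one probably does too and the worst one is lower than stated. Thirty metres is also the SAP's responder threshold (Table 24, item 13), so this corner of the grid is not a trivial one.

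**Working it through.** **Inputs**
- Allocation: subjects are "randomized in a 1:1 ratio into one of two dosing cohorts" (Protocol 8.2).
- Interim at 75 of 150 evaluable patients; second stage 75, or 113 if the total becomes 188.
- Boundaries: p<0.0046 is z=2.6045; p<0.0229 is z=1.9972.
- CHW weights √0.5 each (Protocol 16.5).
- CP from the observed interim difference and SD (SAP 5.4).
- SD levels 50, 60 and 75 from SAP Table 22. Protocol 16.2 gives only the range, so SD 60 is an assumption about the simulated grid.
- The 20% dropout affects only the number randomized.

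**Formulas**
- Mean of the interim statistic: δ√75/(2σ). At 30 m this is 2.165 for SD 60 and 1.732 for SD 75.
- Success at the end needs Z2 > √2×1.9972 − Z1 = 2.8245 − Z1.
- CP = Φ(2·Z1 − 2.8245); flat-prior PP = Φ((2·Z1 − 2.8245)/√2).
- Power = P(Z1 ≥ 2.6045) + ∫ φ(z − mean) · Φ(z − 2.8245 + δ√n2/(2σ)) dz, taken over interim values between the futility and efficacy limits, with n2 = 75 or 113.

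**Checks against the plan's own figures**
- Gamma = −3 spending at half the information gives 0.00456 (plan: 0.0046).
- CP at Z1 = 1.732, 2.165, 2.309 and 2.598 is 0.739, 0.934, 0.964 and 0.991, as in SAP Table 22.
- Where CP at 150 is 57.2% (Z1 = 1.503), CP at 188 is 0.700, which is the SAP's 70%.
- Type I error without futility is 0.0250. The documents say of the criteria: "They are constructed to control overall type 1 error at 0.025, 1-sided". With the CP stop it is 0.0225.

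**Where the stop falls**
- CP = 10%: Z1 = (2.8245 − 1.2816)/2 = 0.77, an observed difference of 10.7 m at SD 60 or 13.4 m at SD 75.
- Flat-prior PP reaches 10% only at Z1 = 0.51, and informative-prior PP only below zero. When either measure can trigger the stop, CP therefore governs whichever PP is meant. The next row of each table also requires CP above 10% to continue.
- P(futility stop | 30 m): Φ(0.7715 − 2.165) = 8.2% at SD 60; Φ(0.7715 − 1.732) = 16.8% at SD 75.

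**Power (%), true difference 30 m**

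| Increase rule | SD 60, no futility | SD 60, CP stop | SD 75, no futility | SD 75, CP stop |
|---|---|---|---|---|
| None, N=150 | 85.9 | 82.8 | 68.0 | 64.3 |
| Protocol Table 7 as written | 86.3–86.9 | 83.2–83.8 | 68.5–69.4 | 64.8–65.8 |
| SAP Table 35 | 87.0–87.4 | 83.9–84.3 | 69.5–70.1 | 65.8–66.5 |
| Whole 30–80% zone on CP to 188 | 88.2 | 85.1 | 71.3 | 67.6 |

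Ranges cover the zone read on CP, on flat-prior PP, or on either. With the whole zone read on either measure, power under the CP stop is at most 86.0% and 68.8%.

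The loss is the same in every row (85.9 − 82.8 = 3.1 points; 68.0 − 64.3 = 3.7 points), because the futility region lies below the increase zone. A t-statistic simulation (400,000 runs per cell) with futility gave 82–83% and 64–65%, or 85% and 67% for the whole-zone rule.

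**Neighbouring cells with the CP stop:** 40 m/SD 75 is at least 87.3% and 30 m/SD 50 at least 93.5%.

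**The case against.** **The match does not prove omission.** A reader might infer that the stated pair can be obtained only by ignoring futility, and so that the simulations left it out. The documents do not support that. They are silent, section 16.2 names futility as a purpose of the interim just before the power sentence, and the simulation output is not in them. Some rules with a stop active also come close:
- futility on flat-prior PP alone, with the whole 30–80% zone (on CP or PP) sent to 188: 87.6% and 70.7%;
- futility on CP, with every continuing trial sent to 188: 87.6% and 71.2%;
- futility on informative-prior PP alone, with the whole 30–80% CP zone sent to 188: 88.2% and 71.3%.

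This stands as a limit on the inference. It does not rescue the stated figures, because none of the three is the written rule. Both tables let CP trigger the stop, Table 7 keeps 150 when 188 is not enough, and neither table sends every trial to 188.

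**The size depends on which measure drives futility.** SAP Table 22 carries two versions of PP and the rule tables do not choose between them. With flat-prior PP alone and no increase, power would be 84.5% and 66.2%. With informative-prior PP alone the stop would cost under 0.1 point. This matters only if the rule is changed from its literal form.

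**SD 60 may not have been simulated.** If only SD 50 and 75 were run, the >87% part survives even the CP stop, and only the ~71% fails. This also stands, as a stated assumption.

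**The consequence is limited.** The shortfall is confined to two pessimistic cells. The prior estimate cited in the SAP is 69.6 m with SD 38.7. Type I error control is unaffected.

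**Conclusion.** The concern holds in this form: the interim rules as written in Protocol Table 7 and SAP Table 35 do not deliver the power stated in Protocol sections 2 and 16.2 and SAP section 5.4. Power is about 83–84% at 30 m/SD 60 and about 64–66% at 30 m/SD 75, and at most about 86% and 69% under the more generous whole-zone increase.

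This rests on three things: the literal reading that either CP or PP triggers the stop, CP computed from the observed interim trend (confirmed by Table 22), and, for the first figure only, SD 60 being on the simulated grid. The figures are a range because the protocol and SAP disagree on the lower edge of the increase zone.

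That the simulations omitted futility is the likely explanation, since the rules closest to the written ones approach the stated pair only without the stop. It remains an inference. The defect that can be shown is a mismatch between the stated power and the stated rules. It should be corrected, but it does not threaten the validity of the test.

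**What to change.** 1. Reconcile the lower edge of the re-estimation zone (30% in Protocol Table 7, 57.2% in SAP Table 35) and the condition for going to 188.
2. State in both tables which CP and which PP (flat or informative prior) drive the futility rule, and whether either one alone triggers the stop.
3. Rerun the simulations with that rule and the futility stop active, on a stated grid of differences and SDs. Give one SD range in both documents (50–75 m in the protocol, 50–70 m in the SAP).
4. Replace the power sentence in the synopsis, Protocol 16.2 and SAP 5.4 with the results, and say there that futility was applied. The figures above show the expected size; they should not be copied in before steps 1 and 2 are settled.

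The cost is a simulation run, the clarifications to the two rule tables and three revised sentences. Power will read less favourably. No extra patients are needed, and the efficacy boundaries stay as they are.

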16.3. Efficacy Analyses

16.3.1. Primary Efficacy Endpoint

The primary endpoint is to evaluate the efficacy of iNO as measured by the placebo-adjusted change in 6-minute walk distance (6MWD) from baseline to 18 weeks. The average of the two 6MWDs at Week 2 (after run-in) will be used as the baseline value for analysis of data. The

6MWD at Week 2 should be obtained on all subjects, even if the subject does not qualify to enter into the treatment phase.

The primary statistical test for the primary endpoint will be performed using a repeated measures mixed model with the baseline stratification factor (i.e., the prostanoid usage status), - treatment arm, week, and treatment-by-week interaction as the main effects. As a covariate, baseline 6MWD assessment will be included in the model. In case the normality assumption is substantially violated (i.e., graphical assessment of residuals from the analysis model and the Shapiro-Wilk test statistic graphical assessment of the residuals from the analysis model and), the primary efficacy endpoint will be analyzed using the van Elteren test stratified by the prostanoid usage status. Least Squares mean differences, standard errors, 95% confidence intervals will be derived from the analysis model.

Exploratory analyses will be performed to evaluate the effects of demographics and baseline characteristics on the efficacy response with appropriate statistical methods. Subgroup analyses based on study drug usage, background therapies, demographics and baseline characteristics, as well as other study compliance status will be conducted. Additional statistical methods such as mixed effects model and Cochran–Mantel–Haenszel (CMH) test (for dichotomized response analysis) may be utilized in the exploratory analyses.

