16.3.5. Handling Missing Data

Missing data imputation for primary endpoint:

For primary analysis, i.e. change from baseline at Week 18, missing data will not be imputed.

The following missing data imputation techniques will be employed for sensitivity analyses of primary endpoint.

- 1) Last Observation Carry Forward (LOCF) approach will be applied for subjects not withdrawing trial due to adverse events, for subjects withdrawing trial due to adverse events (including deaths), worst value (for e.g. zero for 6MWD) will be assigned at EOS visit.
- 2) Worst-case imputation approach I (i.e. impute the missing value for a subject with worst value (within the subject) for all subjects who withdraw prematurely for any reason. The value of zero for 6MWD will be imputed for all deaths.
- 3) Worst-case imputation approach II (i.e., impute the missing value for a subject in the active and Placebo dose group by the worst result of all subjects with non-missing assessments in their respective assigned dose groups). The value of zero for 6MWD will be imputed for all deaths.
- 4) Worst-case imputation approach III (i.e. impute the missing value for a subject in the active dose group by the worst result of all subjects with non-missing assessments in the same active dose groups and impute the missing value for a subject in placebo group by his/her last available assessment prior to the missing assessment. The value of zero for 6MWD will be imputed for all deaths.

Missing data imputation for secondary endpoint:

For all the other efficacy endpoints, the last observation carry forward (LOCF) approach will be used in handling the missing data as that used in the EARLY study ([Galiè 2008](#)).

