**Table 23 Factors/Covariates for Analysis**

Factor/Covariates	Random/Fixed	Type
-------------------	--------------	------

Factor/Covariates	Random/Fixed	Type
Treatment Group	Fixed	Categorical(Two)
Visit	Fixed	Categorical(Four)
Prostanoids usage status	Fixed	Categories(Two)
Baseline 6MWD	Fixed	Continuous
Treatment By Visit Interaction	Fixed	Categorical (Eight)

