### Missing Data Imputation Rules:

Missing data will not be imputed for primary analysis.

The results will be presented in terms of LS means and the difference between LS means, with associated confidence interval and p-value.

Standard descriptive statistics for two separate categories ((1) increase in 6MWD from baseline at Week 18 and decrease in 6MWD from baseline at Week 18) will be presented along with the visit-wise 6MWD.

This analysis will be performed on Intention to treat (ITT), Per-Protocol (PP) and Modified Intention to treat (mITT).

Analysis performed on ITT will be considered as primary.

The within-subject error is assumed to have an unstructured (UN) covariance matrix. However, if the fit of the unstructured (UN) covariance structure fails to converge, then the following options will be tried in order until convergence is reached.

- 1) Toeplitz with Heterogeneity (TOEPH)
- 2) Autoregressive with Heterogeneity (ARH(1))
- 3) Toeplitz (TOEP)
- 4) Autoregressive (AR(1))
- 5) Compound Symmetry (CS)

If model still doesn't converge then this will be highlighted and discussed in the BDR meeting and an appropriate covariance structure to be used will be agreed. The denominator degrees of freedom will be estimated using a Kenward-Roger approximation. The pairwise treatment differences will be estimated as differences between the least-squares means and tested using an F-test based on the Type III sums of squares.

The SAS code for the MMRM analysis is provided below for interim analysis.

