**PROC MIXED Data= 6MWD;**

**CLASS PATID TREAT STRATA VISIT;**

**MODEL CHG = 6MWDBASE TREAT STRATA VISIT TREAT\*VISIT / DDFM=KR OUTPRED=RESID;**

**REPEATED VISIT / SUBJECT=PATID (TREAT) GROUP = TREAT type=UN;**

**LSMEANS TREAT\*VISIT / PDIFF cl;**

**ODS OUTPUT DIFFS=DIFFS1;**

**ODS OUTPUT LSMEANS=LSMEANS1;**

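### The primary MMRM fits one baseline 6MWD slope for all four visits, so the Week 18 contrast may be slightly biased if that slope drifts and baseline-related drop-out differs by arm

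*Protocol*

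**What the plan says.** Protocol 16.3.1 lists the prostanoid stratum, then "treatment arm, week, and treatment-by-week interaction as the main effects. As a covariate, baseline 6MWD assessment will be included in the model". In SAP Table 23 the visit factor has four levels and the only interaction is "Treatment By Visit Interaction". The SAS code in SAP 7.3.1 reads "MODEL CHG = 6MWDBASE TREAT STRATA VISIT", followed by treatment-by-visit, with covariance "GROUP = TREAT type=UN". SAP Table 25 repeats the same factors for the primary analysis and for every MMRM sensitivity analysis. Neither document contains a baseline-by-visit term.

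On missing data, protocol 16.3.5 states: "For primary analysis, i.e. change from baseline at Week 18, missing data will not be imputed". SAP 7.3.1 agrees: "Missing data will not be imputed for primary analysis". Protocol 16.2 notes that "total randomized is higher to account for an anticipated 20% dropout rate".

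Two provisions soften the problem. Protocol 10.1 and 11 encourage subjects who stop study drug to keep attending to Week 18. SAP Tables 24 and 25 add four single-imputation sensitivity analyses and a Week 18 ANCOVA without imputation.

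**The concern.** The model lets the treatment effect vary by visit and leaves the covariance unstructured within each arm, but it holds the effect of baseline 6MWD equal from Week 6 to Week 18. Those visits fall 4 to 16 weeks after the Week 2 baseline. If the correlation with baseline fades over that time, change from baseline depends more steeply on baseline at Week 18 than the pooled slope allows.

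With no imputation, the primary estimate relies on the fitted mean model for subjects without a Week 18 walk. If weaker walkers are lost more often in one arm, a wrong Week 18 slope does not cancel between arms. The error then enters the test that carries the alpha. Because the SAP gives this code for the interim analysis, it also enters the early stopping and sample-size decisions. An unstructured covariance does not repair a misspecified mean.

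**Working it through.** **1. The plan's own figures.** These confirm the design as read.
- Interim alpha under the gamma = -3 spending function at half information: 0.025 × (1 - e^1.5)/(1 - e^3) = 0.025 × 3.482/19.086 = 0.00456 (stated 0.0046). The matching final level is 0.02288 (stated 0.0229).
- Drop-out: 150/0.8 = 187.5, so 188 (stated 188).
- Power at 30 m, SD 75 m: 68.8% for a fixed 75 per arm, and 71.4% by simulation with the protocol's re-estimation zone and the equal-weight CHW statistic (stated about 71%). At 30 m, SD 60 m it is 88.3% (stated above 87%).

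**2. Where bias can arise.** Let b18 be the true baseline slope at Week 18, bp the pooled slope, and m the mean baseline of subjects observed at Week 18 in each arm. Ignoring what is borrowed from earlier visits,

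bias ≈ (b18 - bp) × (m_iNO - m_placebo).

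Either factor can be zero. A constant slope makes the first zero; drop-out with the same rate and the same baseline dependence in both arms makes the second zero. If slopes run evenly from -0.10 to -0.25 and bp is their plain average, b18 - bp = -0.25 - (-0.175) = -0.075, so each metre of imbalance in m is worth about 0.075 m. Losing more low-baseline placebo subjects makes m_iNO - m_placebo negative and the bias positive (favouring iNO). The reverse pattern works against iNO.

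**3. Simulation of the planned model with and without baseline-by-visit.** From the documents: 94 per arm, four visits, unstructured covariance by arm, no imputation. Assumed, because the documents give nothing: no true effect, SD of change 75 m, baseline SD 80 m, monotone drop-out at random, and the slopes and patterns below. Bias is from large samples (Monte Carlo SE about 0.3 m); error is from 2000 trials at 94 per arm, one fixed one-sided test at 0.025.

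| Slope, Week 6 to 18 | Drop-out, placebo / iNO | Bias, one slope → interaction (m) | One-sided error |
|---|---|---|---|
| constant -0.20 | seven patterns | models agree within 0.04 | 0.026 → 0.025 (opposite dependence) |
| -0.10 to -0.25 (mild) | 20/20, same dependence | +0.4 → +0.4 | not run |
| mild | 20/20, placebo dependent only | +0.8 → -0.3 | not run |
| mild | 30/10, placebo dependent only | +1.9 → +0.1 | 0.034 → 0.027 |
| mild | 20/20, opposite dependence | +2.0 → -0.2 | 0.045 → 0.027 |
| 0 to -0.30 (strong) | 30/10, placebo dependent only | +3.4 → +0.2 | 0.036 → 0.019 |
| strong | 20/20, opposite dependence | +4.5 → 0.0 | not run |
| strong | 20/20, opposite, doubled | +7.0 → -0.1 | 0.089 → 0.030 |

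The +0.4 m under equal dependence is the same in both models and is within simulation error. With baseline SD 60 to 100 m, the difference between the two models under mild drift is 1.2 to 2.0 m (30/10, placebo dependent only) and 1.6 to 2.9 m (opposite dependence).

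**4. A second set of assumptions.** 6MWD SD 95 m, single-walk noise 25 m, correlation falling 1.5% per week (slopes -0.09 to -0.24), more drop-out at low baseline. Error = 1 - Phi(1.96 - shift/SD), with SD of the estimate 10.8 m.
- 33/14 drop-out: shift 1.44 m; 1.96 - 1.44/10.8 = 1.827; error 0.034.
- 29/19: shift 0.69 m; 1.96 - 0.69/10.8 = 1.896; error 0.029.
- 25/15, which averages the planned 20%: shift 0.5 to 1.0 m; error 0.028 to 0.031.
- 22/18: shift 0.2 to 0.4 m; error 0.026 to 0.027.
- Reversed, 14/33: shift -1.2 to -2.0 m, against iNO.

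The last three rest on assumed log-odds of drop-out of 0.5 to 1.0 per baseline SD per visit.

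**5. Limits of the added term.** With placebo drop-out depending on the unobserved Week 18 value, the bias was -9.0 m with one slope and -8.7 m with the interaction. With slopes that differ by arm (by 0.2 at Week 18) and 30/10 drop-out, the full-data difference was -0.57 m; one slope gave +0.23 and the interaction -2.4, so the interaction model was about 1.8 m off and the single slope about 0.8 m.

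**The case against.** Nothing in the documents is contradictory or missing here. A single baseline slope is a coherent choice, and no passage shows that the slope drifts, that drop-out depends on baseline, or that it differs by arm. Under the null, a marked difference in drop-out requires iNO to leave 6MWD unchanged yet alter who stays. At the planned 20% average the shift is about 1 m or less in the second set of assumptions; even its 33/14 case is under 5% of 30 m (1.44/30 = 4.8%). The SAP already plans a Week 18 ANCOVA without imputation, which estimates its own Week 18 slope. Attendance after stopping drug is encouraged, so stopping drug need not mean a missing walk.

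Most of this stands and limits the weight of the point. It does not remove it. The ANCOVA is a sensitivity analysis and cannot protect the primary test, and Table 24 items 7 to 11 and 14 reuse the primary model. Equal drop-out rates are not full reassurance either, because opposite baseline dependence at 20/20 also shifts the estimate.

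Three stronger readings are tempting, and the documents do not support them.
- A reader might infer that baseline-dependent drop-out differing by arm biases the contrast by itself. It does not; with a constant slope the bias is zero.
- A reader might infer that the MMRM is the plan's only handling of drop-out. That is true of the primary analysis only.
- A reader might take the error rates above as the trial's. They describe one fixed test, whereas the trial uses 0.0046 at interim and 0.0229 on the CHW statistic. With 1500 replicates in the second set, the Monte Carlo SE near 0.03 is about 0.004, so the shift in metres is the firmer result.

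**Conclusion.** The point holds as a conditional one. The Week 18 contrast may be biased, in either direction, when two conditions meet: the true baseline slope changes between Weeks 6 and 18, and drop-out depends on baseline differently by arm (in rate, strength or direction).

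Under mild drift the size is roughly 0.2 to 2 m, at most about 7% of the 30 m smallest planned effect (2/30) and about one sixth of a standard error of about 12 m. Strong drift or opposite baseline dependence by arm is needed for more. Slopes, baseline SD and drop-out patterns are all assumed, so the size in this trial cannot be fixed from the documents. The change is a free improvement to consider, not a correction of an error.

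**What to change.** Add the baseline 6MWD-by-visit interaction to protocol 16.3.1, SAP Table 23 and the MMRM rows of SAP Table 25, and add 6MWDBASE*VISIT to the MODEL statement, for both the interim and final analyses and before any unblinded look. Report the Week 18 difference at the mean baseline. Keep the Week 18 ANCOVA without imputation as a check.

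The cost is three parameters (four slopes instead of one) and no new data. With constant slopes the mean estimate was unchanged (-0.15 m under both models). Across the scenarios run at 94 per arm, the SD of the estimate was 11.5 to 11.9 m with one slope and 11.3 to 12.1 m with the interaction. Sample size and planned power stay as they are.

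The SAP should not present the term as a remedy for drop-out in general. It protects under missing-at-random with a linear slope common to both arms; it does not address informative drop-out or arm-specific slopes.
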